6.3. Data Analysis

6.3.1. Preparatory steps

Behavioural data of all measures will be combined to specific sum scores or mean scores, as required. Missing data will be evaluated to determine potential estimation bias. If the data is MAR multiple imputation will be used to model the influence of missingness. Where missingness demonstrates other properties, other methods of sensitivity analysis will be considered.

6.3.2. Primary analyses

Pilot Study

The pilot study has one primary research question:

- Can routinely collected data at baseline (passive sensory data, or psychometric measures) predict which intervention will be more effective for an individual (based on baseline assessments and machine learning (ML) algorithms).

A secondary research question is

How effective are each of the active interventions at reducing PUI risk compared to the control group.

The pilot study will include three groups, Emotional Regulation intervention, Inhibitory Control intervention and a control group. A fourth validation group for testing the ML algorithm will be drawn as a random sample of 1/3rd of participants from each study arm, resulting in a total sample size of 4 × 838 = 3,352 participants. All other analyses will be secondary and evaluated using General Linear Models (GLM).

Behavioural data from all measures will be aggregated into sum scores or mean scores as appropriate. Efficacy evaluation will be conducted using General Linear Modelling, accounting for demographic and psychological variables. The primary analysis will focus on between-group comparisons, estimating group differences with 95% confidence intervals and calculating effect sizes.

Machine Learning Approach

To predict psychological phenotypes from multisource big data, we will apply a rigorous ML approach underpinned by psychological theory (Montag & Rumpf, 2021). The pilot study data will be used to develop predictive algorithms identifying which individuals are most likely to benefit from the emotional regulation intervention or the inhibitory control intervention.

We will build multivariate predictive models using both classical methods (logistic regression, support vector machines (SVMs), Random Forest, boosted trees (XGBoost)) and advanced techniques (deep neural networks, domain adaptation, deep representations, adversarial training). These models will link assessment data to individual-level outcomes, incorporating risk assessments from the assessment study alongside a range of input dimensions, including:

- Digital behaviour: Repetitive patterns, diurnal variation, app usage types
- Neurological assessments: Reaction time, error ratio
- Personality dimensions: Compliance rate, communication patterns

Learning Representations

We will build upon the representations developed in the assessment study, expanding them to include new data dimensions and integrate predicted risk assessments. Both supervised and unsupervised methods will be utilised, with a focus on model expandability.

Downstream Predictive Modelling

A hybrid approach combining classical and advanced deep learning methods will be applied, following consistent modelling strategies. To address site biases, multi-source domain adaptation will be used, as in the assessment study. Given that treatment outcomes might be influenced by site-specific factors, leave-one-site-out cross-validation will ensure models generalise to new sites while controlling for confounding factors.

To identify actionable variables for interventions, we will apply SHAP (SHapley Additive exPlanations) to evaluate the contribution of individual variables to overall predictions.

Generalisation and Validation

We will use standard methods to assess model generalisation and validation. Once the learning phase is complete and the final predictive performance is established, hypothesis testing will be conducted on the fourth (validation) group. This approach aligns with best practices in eHealth application development, ensuring robustness and practical applicability.

Randomised Control Trial

The RCT has 3 primary research questions:

- Is the intervention (ignoring allocation method) effective (by comparison to control) [2:1 allocation].
- Is tailored allocation more effective than random allocation irrespective of the intervention?
- Is the emotional regulation intervention more effective than the inhibitory control intervention irrespective of allocation method.

These analyses specify 3 groups per analysis, requiring a sample size of $3*838=2514$ in total. All other analyses are secondary and will be evaluated using appropriate GLM models.

Behavioural data of all measures will be combined to specific sum scores and/or mean scores, as recommended in the specific previous studies and scale descriptions. Evaluation of efficacy will proceed using General Linear Modelling adjusting for a range of demographic and psychological variables. The primary comparison will be between groups to allow group differences (with 95% confidence intervals) to be estimated along with the effect size (with a confidence interval). Each of the 3 primary questions will be considered in turn.

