3.4.2. Sample size, basic assumptions

The pilot study and the RCT study are the second and the third in a series of three studies building upon each other, which will be conducted within the BootStRaP project. Therefore, considerations regarding sample size and power estimates include the prospect of interventions introduced in subsequent studies. As yet, there is little evidence of the effectiveness of this kind of intervention on PUI (specifically as measured by the PIUQ).

For the pilot study we assume $\alpha=0.05$, $1-\beta=0.8$, and a small effect size $d=0.3$, giving a required sample size $n=176$ per group. We assume 70% of randomised young people will complete follow-up. We also assume that 30% of children are high risk. To provide a cohort of 176 high risk children followed up requires a total sample of $n=838$ per group ($n=176/0.3/0.7$). The pilot study assumes 3 groups (random allocation to the Emotional regulation intervention, the Inhibitory control intervention, and a control groups). A 4th group of equivalent size to each study arm is required for validation of the algorithm developed in the machine learning phase; this group will be drawn at random from the sample allocated to each study arm. This giving a total sample size of $4*838= 3352$, or 373 per study site. All other analyses are secondary and will be evaluated using appropriate GLM models.

For the RCT, we assume $\alpha=0.05$, $1-\beta=0.8$, with cluster size=30 and effect size $d=0.3$, requiring $n=176$ per group. To allow for 70% completion, and 30% of children at risk, the total per group $N=838$. For the trial the sample size is $3*N=2514$ or 279 per study site.

4. Study Procedures

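### Pilot: drawing one third of each arm for validation does not give the four groups of 838 on which the sample size rests; that needs a one-quarter draw

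*Protocol*

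**What the plan says.** Section 3.4.2 builds the pilot sample size from a two-group comparison with α = 0.05, power 0.8 and d = 0.3, which gives 176 per group. It then inflates this on two assumptions: "We assume 70% of randomised young people will complete follow-up" and "We also assume that 30% of children are high risk". The result is 838 per group.

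The section next adds a validation set: "A 4th group of equivalent size to each study arm is required for validation of the algorithm developed in the machine learning phase". These people are not recruited in addition, because "this group will be drawn at random from the sample allocated to each study arm". The total is given as 4 × 838 = 3,352.

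Section 4.5 gives each pilot participant an equal chance of one of three groups. There is no fourth randomised arm.

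Section 6.3.2 fixes the size of the draw: "A fourth validation group for testing the ML algorithm will be drawn as a random sample of 1/3rd of participants from each study arm". The same sentence says that this results in 4 × 838 = 3,352. Under Generalisation and Validation, the section adds that, after the learning phase, "hypothesis testing will be conducted on the fourth (validation) group".

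The Study Summary gives a planned sample of 3,600 per cohort.

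**The concern.** The fraction drawn and the total sit in one sentence and cannot both be followed. If one third of each arm is set aside, the remaining arms are smaller than 838 and the validation group is larger. The groups are then neither equal nor of the size that the calculation requires.

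Two things are at stake. First, the split defines which data train the algorithm and which data test it, so the team needs one unambiguous fraction before the split is made. Second, the sizing asks for 176 followed-up high-risk participants in each group. If the validation participants are not counted in the arms, which is how the four-group sizing treats them, the pilot misses that target under its own assumptions.

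**Working it through.** **Inputs.** From section 3.4.2: α = 0.05, power 0.80, d = 0.3, 70% completion, 30% high risk, 838 per group, total 3,352. From section 4.5: 1:1:1 allocation to three arms. From section 6.3.2: a one-third draw from each arm. From the Study Summary: 3,600 planned. The protocol does not state sidedness; a two-sided test is assumed because it reproduces the stated n (a one-sided test would need 138).

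**Step 1: reproduce the plan's figures.**
- n per group = 2(1.96 + 0.842)² / 0.3² = 175 by the normal approximation. The t-test version gives 175.4, rounded up to 176.
- 176 / 0.3 / 0.7 = 838.
- 4 × 838 = 3,352, and 3,352 / 9 sites = 372.4, which the protocol gives as 373 per site.
- Power at 176 per group is 80.1% (t-test) or 80.4% (normal).

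The stated sample size is therefore sound on its own terms.

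**Step 2: apply the draw.** Randomised per arm: 3,352 / 3 = 1,117.3.

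| Draw from each arm | Removed per arm | Left per arm | Validation group |
|---|---|---|---|
| 1/3 (as written) | 372.4 | 744.9 | 1,117.3 |
| 1/4 | 279.3 | 838.0 | 838.0 |

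Only the one-quarter draw gives four groups of 838. To keep 838 per arm after a one-third draw, the total would have to be 3 × 838 × 3/2 = 3,771, which exceeds both 3,352 and the planned 3,600.

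**Step 3: effect on the sizing target.** High-risk completers per arm = number analysed per arm × 0.3 × 0.7. Normal-approximation power = Φ(d√(n/2) − 1.96). For example, at n = 156.4: 0.3 × √78.2 − 1.96 = 0.693, and Φ(0.693) = 75.6%. The table gives the t-test value first.

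| Total | Participants in the arm comparison | Per arm | High-risk completers per arm | Power at d = 0.3 |
|---|---|---|---|---|
| 3,352 | after 1/4 draw | 838 | 176.0 | 80.1% (80.4%) |
| 3,352 | after 1/3 draw | 745 | 156.4 | 75.3% (75.6%) |
| 3,600 | after 1/3 draw | 800 | 168.0 | 78.3% (78.5%) |
| 3,352 | all randomised | 1,117 | 234.6 | 90.0% (90.1%) |

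The result therefore depends on whether the held-out participants are counted in the comparison, and the protocol does not say.

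**The case against.** **The power loss is conditional.** A reader might infer that the pilot's 80% power simply becomes 75%. The documents do not support this without conditions. A hold-out has to be kept out of model training only, and no section says that the effectiveness model leaves it out. With full arms, power is about 90%. Even with exclusion, the shortfall is under two points if 3,600 are recruited. This stands, so the 75% must be stated with its conditions.

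**The comparison is secondary and the target is a subgroup.** Section 2.1 makes effectiveness a secondary objective of the pilot. The Figure 1 caption has the high- and low-intensity versions analysed together, and section 6.3.2 does not restrict the model to high-risk participants. With 745 per arm, completers of any risk number 745 × 0.7 = 521 per arm, and power at d = 0.3 is 99.8%. This also stands. The loss concerns the high-risk target that sets the sample size, not the primary prediction question.

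**The fraction may be a slip.** If one third of the validation group comes from each arm, that is 838 / 3 = 279 per arm, leaving 838, and everything agrees. That is plausible but is not what the sentence says. Another reading, one third of arms of 838, leaves 559 per arm, a total of 2,514 and about 63% power; it contradicts 3,352. It can also be said that a validation group of 1,117 equals one arm as randomised. That reconciles the equal-size wording of section 3.4.2 but not the product 4 × 838.

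**Two stronger readings about validation fail.** A reader might infer that the test in the validation group decides whether the algorithm enters the RCT. No section states such a rule; sections 3.3 and 4.5 simply apply the pilot algorithm. A reader might also infer that this test is underpowered. Section 6.3.2 names no contrast or effect size for it, so any power figure would rest on assumptions from outside the document. The one-third draw as written also makes the validation group larger than planned, not smaller.

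**Conclusion.** The contradiction is certain. With 3,352 randomised equally to three arms, a one-third draw gives groups of 745, 745, 745 and 1,117, not four of 838. A one-quarter draw is the fraction that matches the stated total. The protocol itself fixes this figure and fixes it inconsistently, so it is not a detail left to a later analysis plan.

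The consequence is moderate and conditional. If held-out participants are excluded from the comparison with control, high-risk completers fall from 176 to 156 per arm and power from 80% to 75% (78% at 3,600). If they are included, power is about 90%. These figures rest on the protocol's own 70% completion, 30% high risk and d = 0.3, on a two-sided test, and on a two-group comparison among high-risk completers. They do not describe the power of the pilot's primary prediction question.

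**What to change.** 1. In section 6.3.2, change the fraction drawn from each arm to 1/4, so that it agrees with section 3.4.2 and the total of 3,352. Alternatively, keep 1/3 and restate the sizes and power in both sections: 745 per arm, 1,117 for validation, and 75% power in high-risk completers if the validation group is excluded from the arm comparison.
2. State that validation participants are excluded from model training only and are included in the secondary effectiveness model, which then has 1,117 per arm and about 90% power in high-risk completers. With this sentence, the fraction no longer affects the power of that model; it determines only how the data divide between training and validation.

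The cost is one number and one or two sentences, with no added recruitment. The one-quarter draw has a small downside: the validation group is 838 instead of 1,117. Either way, the choice should be made before the split is drawn.

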Study Objective(s)	
The aim of this phase of the study, which incorporates both a pilot study (cohort 2) and an RCT (cohort 3), is to investigate two promising theory-informed candidate preventative interventions, targeting A: emotional regulation and B: inhibitory control, for Problematic Use of the Internet (PUI).
 
For the Pilot study: The primary objective is to use participants' individual characteristics to build models for predicting that predict outcomes for both novel preventative interventions when compared to a control condition (non-interactive provision of information on PUI).
 
The secondary objective is to explore the effectiveness of each preventative intervention compared to a control condition when allocated at random.
 
For the RCT: The primary objective is to evaluate the effectiveness of the predictive models derived from the pilot. We achieve this by comparing the effectiveness of each intervention (i.e., targeting emotional regulation or inhibitory control) when allocated either according to an algorithm derived from individual baseline outcome predictors (tailored arm), or when allocated at random (random arm) versus a control condition (non-interactive provision of information on PUI).
 
The secondary objective is to evaluate and compare the cost-effectiveness and cost utility of both allocation methods (tailored, random), investigating feasibility for large-scale implementation.

Planned Sample Size	3,600 (approximately 400 young people at each site), per cohort.
Participants	Young adolescents aged 12-16

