2.1. Study objectives

The second phase of the BootStRaP project aims to evaluate two promising, theory-informed preventative interventions for Problematic Usage of the Internet (PUI). This phase consists of a pilot study and a randomised controlled trial (RCT), designed to refine intervention strategies and optimise participant allocation.

Pilot Study

The primary objective of the pilot study is to identify key predictive characteristics that determine individual responses to the two interventions (emotional regulation and inhibitory control), compared to a control condition (non-interactive provision of psychoeducation on safe and effective use of the internet).

The secondary objective is to assess the overall effectiveness of each intervention relative to the control group under random allocation.

We do not expect one intervention to be superior to the other; rather, both are anticipated to be more effective than the control condition in reducing PUI risk. However, the primary focus is not on comparative effectiveness but on developing algorithms for personalised intervention matching, which will be applied in the subsequent RCT.

Randomised Control Trial

The primary objective of the RCT is to determine whether tailored intervention allocation (matching participants to either the emotional regulation intervention or inhibitory control intervention, using machine learning algorithms developed in the pilot study) leads to better outcomes compared to random allocation to the emotional regulation intervention or inhibitory control intervention or the control arm.

The secondary objective is to evaluate the cost-effectiveness and cost utility of this tailored approach, ensuring feasibility for large-scale implementation.

This structured approach will provide crucial insights into optimising individualised intervention strategies for preventing PUI in adolescents.

3. Methods

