4.5. Randomisation

In both the pilot and RCT studies, randomisation will be carried out using individualised, server-based assignment, based on each participant's access code at registration.

Pilot study: For the pilot study each participant will have an equal probability (33.3%) of being allocated to one of the three groups: Emotional regulation intervention group, Inhibitory control intervention group, or the control group.

RCT: For the RCT, each participant will have an equal probability (33.3%) of being allocated to one of three arms: tailored allocation, random allocation, control. This means that participants will have a 66.6% chance of allocation to an active intervention and 33% chance of allocation to the control arm.

Participants allocated to the random allocation arm will have a 50% chance of receiving the emotional regulation or inhibitory control intervention.

In the tailored allocation arm, participants will receive the intervention (targeting emotional regulation or inhibitory control) predicted as most likely to be effective for them by comparing their baseline profile (against the profile of response-predictors developed during the pilot study).

For both the pilot study and the RCT, both participants and researchers will remain blinded to the group allocation to minimise bias. The statistical analysis will be completed on blinded data (allocation A, B or C), with the blinding only being broken when the primary analysis has been completed.

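### The RCT's third primary question compares the two interventions across both allocation arms, but only the random arm randomises them, so the pooled contrast is open to confounding

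*Protocol*

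**What the plan says.** Section 6.3.2 (Randomised Control Trial) sets three primary questions: active intervention versus control, tailored versus random allocation, and "Is the emotional regulation intervention more effective than the inhibitory control intervention irrespective of allocation method". It adds that "Each of the 3 primary questions will be considered in turn", using a General Linear Model adjusted for demographic and psychological variables that it does not name. It applies one total, 3 × 838 = 2514, to all three.

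Section 4.5 describes two stages of allocation. First, "each participant will have an equal probability (33.3%) of being allocated to one of three arms: tailored allocation, random allocation, control". Then the two active arms differ:

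- Random arm: "Participants allocated to the random allocation arm will have a 50% chance of receiving the emotional regulation or inhibitory control intervention".
- Tailored arm: the intervention is the one "predicted as most likely to be effective for them by comparing their baseline profile" with the response predictors found in the pilot.

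The Study Summary says that tailored participants are allocated "according to an algorithm derived from individual baseline outcome predictors (tailored arm"). Nothing in the protocol limits the third question to the random arm.

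**The concern.** In the tailored arm, ER and IC recipients differ by design: they were sorted on variables selected for their relation to outcome. With equal arms, about half of the participants entering the third comparison were sorted in this way. If the profile predicts outcome whichever intervention is given, or if it changes response to one intervention more than to the other, the pooled difference mixes that sorting with any real ER-IC difference.

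An adjustment for allocation arm would not help, because the imbalance lies within the tailored arm. The planned covariates may catch part of it. However, the algorithm's inputs listed in section 6.3.2 include digital behaviour and reaction-time measures, which a demographic and psychological set need not contain.

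At stake is a primary conclusion that one intervention is better, which could reflect how the algorithm sorted participants.

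**Working it through.** **The plan's own size.** Inputs from section 3.4.2: alpha 0.05 (taken as two-sided), power 0.80, d = 0.3, 70% completion, 30% at risk.

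- n per group = 2(1.96 + 0.8416)²/0.3² = 174.4, so 175. The t-test version gives 175.4, rounded up to the stated 176.
- 176/0.3/0.7 = 838.1, stated as 838; 3 × 838 = 2514. The stated figures reproduce.

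**Bias of the pooled contrast.** Assumptions, none from the protocol: one normally distributed profile with correlation r to the outcome, a tailored split at its median, no true ER-IC difference, no covariate adjustment.

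- Difference between the two halves of the tailored arm: 2√(2/π) × r = 1.596r SD.
- Difference in the random arm: 0.
- The arms are equal in size, so pooled bias = 1.596r/2 = 0.798r SD.
- The standard error is √(2/n) with n per intervention. For all completers, n = 838 × 0.7 = 587 and the standard error is 0.0584. For high-risk completers, n = 838 × 0.3 × 0.7 = 176.

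| r | Bias (SD) | Rejection at 5%, 587 per group | Rejection at 5%, 176 per group (simulated) | Random arm alone |
|---|---|---|---|---|
| 0 | 0 | 5% | 5% | about 5% |
| 0.1 | 0.08 | 28% | 11% | about 5% |
| 0.2 | 0.16 | 78% | 32% | about 5% |
| 0.3 | 0.24 | 98% | 61% | about 5% |

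Example: at r = 0.2, bias/SE = 0.160/0.0584 = 2.73, and P(Z > 1.96 − 2.73) = 0.78. In simulation, adding allocation arm as a covariate left these results essentially unchanged.

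**Effect modification without prognosis.** Suppose r = 0, the profile changes response to ER only, by an assumed 0.3 SD per SD of profile, and the average ER-IC difference is zero. The tailored ER group is shifted by 0.3 × 0.798 = 0.24 SD and its IC group by 0. Pooling halves this to 0.12 SD, with about 53% rejection at 587 per group. If the modification is instead symmetric between the interventions and the cut is central, the bias is zero.

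**Size of the randomised comparison.** The random arm gives 838/2 = 419 per intervention.

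- High-risk completers: 419 × 0.21 = 88 each. 0.3/√(2/88) = 1.99, so power is about 51%; d = 0.42 is detectable at 80%.
- All completers: 419 × 0.7 = 293 each. 0.3/√(2/293) = 3.63, so power is about 95%; d = 0.23 is detectable at 80%.

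**The case against.** The best reply is that covariate adjustment is planned and can work. A reader might infer that it cannot, since nobody in the tailored arm receives the intervention not recommended. That inference fails because the question pools both arms. With equal arms, the chance of receiving the recommended intervention is 0.5 × 1 + 0.5 × 0.5 = 0.75, and of the other 0.25, so every profile has overlap. In simulation, adjusting for the algorithm's recommendation brought bias to about zero and rejection to about 5%. Linear adjustment for the score left a modest error in one case, with assumed effect modification and an off-centre cut: 0.12 against a true 0.15. This part of the reply stands, but the protocol does not commit to that adjustment.

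The error rates above are unadjusted, depend on an assumed r, and vanish at r = 0 without effect modification. The algorithm aims at differential benefit, which need not track prognosis. That also stands: the figures show how the pooled contrast can fail and do not forecast the trial's error rate.

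The exact covariate list may properly sit in a statistical analysis plan that is not shown. The point here is different: the protocol itself fixes the pooled contrast as primary.

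**Conclusion.** The concern holds in this form: as worded, the third primary question is answered by a contrast that is only partly randomised, and the stated covariates are not designed to remove the resulting confounding. The bias runs from 0 to about 0.24 SD over the assumed range r = 0 to 0.3, without adjustment and with an even split. The first two primary questions compare randomised arms and are not affected.

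Three stronger readings are not supported.

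- That the planned 80% power is missing altogether. The shortfall to about 51% applies on the high-risk basis used for sizing in section 3.4.2. Section 6.3.2 does not restrict the analysis to that group, and all completers in the random arm give about 95% at d = 0.3.
- That the protocol contradicts itself by expecting no difference. The words "We do not expect one intervention to be superior to the other" stand under the pilot objectives in section 2.1. The RCT objective in the Study Summary does mention comparing the effectiveness of each intervention.
- That three primary questions prove an uncontrolled error rate. Alpha appears only in the sizing text, section 6.3.2 describes estimates with 95% confidence intervals, and multiplicity rules are commonly left to the analysis plan.

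**What to change.** In section 6.3.2, define the ER versus IC estimate as the randomised contrast within the random allocation arm. If a pooled estimate is kept, label it supportive and partly non-randomised, and adjust it for the algorithm's recommendation or score, computed from baseline data in both arms by the same rule.

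Restate the size of this comparison beside the 3 × 838 figure: 419 randomised per intervention, with 88 high-risk completers each (about 51% power at d = 0.3) or 293 completers each overall (about 95% at d = 0.3, 80% at d = 0.23). Say which population the question refers to.

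The cost is a change of wording, computing the recommendation for random-arm participants if the pooled estimate is kept, a smaller sample for this question and a less favourable stated power. Keeping 176 high-risk completers per intervention would instead need a random arm of about 2 × 176/0.3/0.7 = 1676 in place of 838; the fix does not require this.

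### The RCT names three primary questions with no testing order or alpha split, giving about a 13–14% chance of at least one false primary result, and its stated primary objective covers only part of them

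*Protocol*

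**What the plan says.** Protocol section 6.3.2, under Randomised Control Trial, states: "The RCT has 3 primary research questions". They are:

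1. "Is the intervention (ignoring allocation method) effective (by comparison to control) [2:1 allocation"
2. "Is tailored allocation more effective than random allocation irrespective of the intervention"
3. "Is the emotional regulation intervention more effective than the inhibitory control intervention irrespective of allocation method"

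All other analyses are declared secondary. Each primary question is to be answered by a group difference with a 95% confidence interval and an effect size with its interval. On how the three relate, the section says only "Each of the 3 primary questions will be considered in turn".

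Section 3.4.2 gives one set of error rates for the RCT: "we assume $\alpha=0.05$, $1-\beta=0.8$, with cluster size=30 and effect size $d=0.3$, requiring $n=176$ per group". This is then inflated to 838 per group and 2,514 in total.

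The Study Summary describes one RCT primary objective: "The primary objective is to evaluate the effectiveness of the predictive models derived from the pilot". It is to be met by comparing algorithm-based and random allocation against control. Section 2.1 likewise gives one objective: whether tailored allocation gives better outcomes than random allocation or control. The legend to Figure 3 (section 3.3) adds that the two interventions are analysed together within an arm, because interest lies in the allocation method.

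**The concern.** Three comparisons on the same outcome in the same trial are all labelled primary. Nothing says that a later one depends on an earlier one, and nothing divides the 0.05. Taking questions in turn describes an order of work, not a condition for testing. If each interval is read at its nominal level, the trial has three separate chances of a false primary finding.

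The protocol also disagrees with itself about what is primary. The objective in the Study Summary and section 2.1 concerns allocation method. A comparison of the two interventions with each other is not part of it, yet section 6.3.2 gives that comparison equal standing. Question 1 also pools the tailored and random arms, whereas section 2.1 sets tailored allocation against control.

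This matters because the Study Summary calls the trial definitive, and sections 6.3.3 and 8.1.1 link the project to wide adoption and European policy recommendations. If just one of the three intervals excluded zero, the protocol would not settle whether the trial had met its primary aim.

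**Working it through.** **Inputs.** From section 3.4.2: alpha 0.05, power 0.80, d = 0.3, n = 176 per group, 70% completion, 30% at risk, 838 per group. From section 6.3.2: three primary questions, 95% intervals, total 2,514. From the Study Summary: planned sample 3,600 per cohort.

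**Step 1: reproduce the plan's figure.** The normal formula is n = 2(z₀.₉₇₅ + z₀.₈₀)²/d² = 2(1.960 + 0.842)²/0.09, which rounds up to 175. The t-test version gives 175.4, hence 176. Then 176/0.3/0.7 = 838 and 3 × 838 = 2,514. A one-sided 0.05 would give 138. A three-way split (0.05/3 = 0.0167) would give 233 by the normal formula or 235 by the t-test. So 176 corresponds to one two-group comparison using the whole two-sided 0.05.

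**Step 2: how the three contrasts are related.** Assume equal arms, equal variances and independent observations.
- Question 1 compares the mean of all active participants with control. Questions 2 and 3 are contrasts within the active participants. Question 1 is therefore uncorrelated with both.
- Let p be the share of the tailored arm sent to one of the two interventions; the random arm splits 50/50. The correlation of questions 2 and 3 is (p − 0.5)/√[(p + 0.5)(1.5 − p)]. It is 0 at p = 0.5, 0.2/√(1.2 × 0.8) = 0.20 at p = 0.7, 0.4/√(1.4 × 0.6) = 0.44 at p = 0.9, and 0.5/√0.75 = 0.58 at p = 1.

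**Step 3: chance of at least one false rejection, all three nulls true.** For independent tests it is 1 − 0.95³ = 14.3%. Simulating the three contrasts (2,000,000 draws per row) gives:

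| Share of tailored arm sent to one intervention | Correlation of questions 2 and 3 | At least one false rejection |
|---|---|---|
| 50% | 0.00 | 14.3% |
| 70% | 0.20 | 14.1% |
| 90% | 0.44 | 13.8% |
| 100% | 0.58 | 13.4% |

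So the figure is about 13–14% whatever the algorithm does.

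**Step 4: favourable direction only.** With 0.025 in one pre-named direction per question and independent tests, 1 − 0.975³ = 7.3%, against 2.5% for a single question.

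**Step 5: what each remedy would do.**
- *Bonferroni at 0.0167.* Familywise error is 1 − (1 − 0.0167)³ = 4.9%. It needs 233 to 235 per group, which is 233/0.21 ≈ 1,110 to 235/0.21 ≈ 1,120 randomised per group, or about 3,330 to 3,360 in total. That is above 2,514 but below 3,600. Kept at 176 per group, power for a 1:1 question falls from 80% to 66%.
- *Making question 3 secondary and nothing else.* Questions 1 and 2 are uncorrelated, so 1 − 0.95² = 9.75% remains.
- *Fixed sequence, each test at two-sided 0.05.* A false confirmatory claim requires rejecting the first true null in the sequence, so the rate is at most 5%. Sample size does not change.

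**Step 6: what the order costs, at 176 per arm.**
- Pooled test (352 versus 176), standard error √(1/352 + 1/176) = 0.0923. At d = 0.3, 0.3/0.0923 − 1.96 = 1.29, so power is 90%.
- Illustration with assumed effects against control of 0.30 (tailored) and 0.15 (random). The pooled effect is 0.225, and 0.225/0.0923 − 1.96 = 0.48, so power is about 68%. The tailored-versus-random difference is 0.15 with standard error √(2/176) = 0.107; 0.15/0.107 − 1.96 ≈ −0.55, so power is about 29%.

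**The case against.** The strongest reply is that multiplicity rules are commonly left to the SAP, which was not available here, and that a fixed sequence could be added there without contradicting the 176 or the 2,514. That is true of the mechanism. It does not dispose of the point, because the protocol itself names the three primaries, sets alpha and sizes the trial, and states a primary objective that does not match its list of primary questions. A SAP should not have to decide which of two protocol statements governs.

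A second reply is that these are distinct questions (any effect, allocation method, content), and that adjusting across distinct questions is debated. This stands as a position, but the protocol does not take it, and the three questions share one outcome and overlapping participants.

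Several stronger readings are tempting, and the document does not support them:
- *That the protocol lets any one question be claimed at p < 0.05.* It states no such success rule. The 0.05 appears as a sample-size assumption, and section 6.3.2 speaks of estimates and intervals. The gap is that nothing prevents such a claim.
- *That nothing indicates which question decides the trial.* The Study Summary and section 2.1 do point to allocation method. Section 6.3.2 does not follow them.
- *That 14% is the chance of a false claim of benefit.* It counts errors in both directions. The favourable direction alone gives about 7%, against 2.5%.
- *That the printed order should simply become the testing order.* That would make the stated tailoring objective depend on the pooled test, which is a choice for the sponsor.

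**Conclusion.** The point holds. As written, three unadjusted primary comparisons carry a 13–14% chance of at least one false rejection when none of the three effects exists, or about 7% against 2.5% in the favourable direction. Either way this is close to three times the nominal level. The figures assume that all three nulls are true, arms are equal and observations are independent. They barely depend on how the algorithm divides the tailored arm. The same sections also contradict each other on which questions are primary. A reader might infer that the trial is too small or that 0.05 must be split; neither follows, since ordering the tests controls the error at the stated sample size.

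**What to change.** First, reconcile section 6.3.2 with the Study Summary and section 2.1, so that the primary questions follow from the primary objective, including whether the comparison with control is for the tailored arm or for both active arms pooled.

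Second, replace the sentence about taking the questions in turn with a fixed sequence, set before any RCT data are seen, each test at two-sided 0.05 on PIUQ-SF-9 at T1. The sponsor chooses whether tailored versus random or pooled active versus control comes first. Emotional regulation versus inhibitory control goes last or becomes secondary. After the first non-significant result, the remaining questions are reported as estimates with 95% confidence intervals and are not confirmatory. Section 6.1.1 also calls the S-CIUS the primary outcome measure, so that wording must be aligned for the rule to rest on one outcome.

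The cost is a few sentences of text and no extra participants. The 176 per group and 2,514 total are unchanged by this rule. The real price is that a later question loses confirmatory status if an earlier one fails. With the assumed pooled effect of 0.225 and 176 per arm, a pooled test placed first would fail about a third of the time (power about 68%). Under the same assumed effects, tailored versus random placed first would fail more often (power about 29%). The sponsor should weigh that against which question the trial exists to answer.
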